8.1 Primary Objective

To obtain characteristics of subjects with WT RAS non resectable mCRC receiving panitumumab in combination with chemotherapy as a 1st line treatment, and to describe the patterns of treatment, including 1st and 2nd line therapies.

8.2 Secondary Objectives

- To assess the response to 1st line treatment.
- To explore the relationship between death and/or disease progression and subject / country characteristics.
- To characterize the group of subjects with ETS outcome (if available).
- To assess incidence of adverse drug reactions (ADR).

8.3 Exploratory Objectives (if available)

9. Research Methods

This is an observational study and thus real world data will be extracted from medical files and collected prospectively.

9.1 Study Design

This is a multicentre, ambidirectional (retrospective-prospective), observational study in the selected European countries, including but not limited to Austria, Bulgaria, Croatia, Czech Republic, Hungary, Poland, Slovenia, Romania and Russia.

The Study Design Schema is presented in Figure 1. In general, to gather the most comprehensive and recent data, the study consists of 3 phases: Retrospective Period, Prospective Observation and Safety Follow-up. Retrospective data will be collected from

Date: 29 April 2019 Page 22 of 64

1 to a maximum of 12 months preceding enrolment, Prospective Observation will be led by a maximum of 15 months and a Safety Follow-up of 30 days after the end of the observation, giving a total of a maximum 28 months of mCRC management data.

Subjects with initially non resectable WT *RAS* mCRC receiving panitumumab in combination with chemotherapy as first-line treatment will be eligible for the study. The decision on treatment with panitumumab should have been taken independently and prior to the decision to study enrolment.

Study participants must have received at least one dose of panitumumab in combination with chemotherapy between 1 and 12 months before enrolment (defined as the informed consent [ICF] signature date). Panitumumab as a 1st line treatment in combination with

chemotherapy should be ongoing at enrolment. Therefore, the Retrospective phase will last a maximum of 12 months for an individual subject. An Interactive voice response system (IVRS) system will be used for enrolment. Baseline data including demographics, characteristics and subjects' clinical information will be collected retrospectively from medical records up to the point of enrolment. From the enrolment point, prospective data will be recorded. The Prospective phase will consist of two periods: 1) observation during the 1st line treatment administration and 2) observation after the end of 1st line treatment. The maximum duration of the Prospective phase will be 15 months. In case of a change in therapy and 2nd line treatment implemented, subjects will enter into the Safety Follow-up phase.

Safety Follow-up will last approximately 30 days after the start of 2nd line treatment, or after 15 months of observation if panitumumab was administered in the last 4 weeks of observation, whichever occurs first, except for death, withdrawal of consent or lost to follow-up. If a subject receives panitumumab in combination with chemotherapy for 15 months, then 30 days of Safety Follow-up will be the 16th month of observation.

Date: 29 April 2019 Page 23 of 64

Table 2. Objectives and Outcomes

Objectives	Outcomes	Exposure variables
Primary		
To obtain characteristics of subjects with WT RAS non resectable mCRC receiving panitumumab in combination with chemotherapy as a 1 st line treatment.	 Demographics Disease history, including location of tumour (left vs. right side) Current status of disease 	Country Total
To describe the patterns of treatment , including 1 st and 2 nd line therapies.	 1st line treatment Any changes during 1st line treatment, including dose, infusion schedule, and reasons for changes Type of progression leading to 2nd line choice Type of 2nd line treatment (type of anticancer therapy) 	 Country Location of tumour (left vs. right side) Oxaliplatin-based chemotherapy Irinotecan-based chemotherapy Total
	 Dose, schedule and reason for treatment selection Subsequent treatment line/approach 	D 1

Page 1 of 2

Date: 29 April 2019 Page 24 of 64

Objectives	Outcomes	Exposure variables
Secondary		
To assess the response to 1 st line treatment described by: the relationship between death, disease progression, ETS (if available), and subject characteristics with the particular interest in tumour location	 Death Disease Progression Response rate Rate of conversion to resectable mCRC Tumour markers: CEA and CA 19.9 Early tumour shrinkage (if available) 	Country Location of tumour (levs. right side) Current disease status Oxaliplatin-based chemotherapy Irinotecan-based chemotherapy Total
To assess incidence of adverse drug reactions (ADR) events (general)	ADR reports: type and duration of ADR incident	Country Total
Exploratory (if available)		

Date: 29 April 2019 Page 25 of 64

9.2 Setting and Study Population

It is planned to include approximately 600 subjects with initially non resectable WT *RAS* mCRC receiving panitumumab in combination with chemotherapy as 1st line treatment. The observations will be conducted in the selected European countries. Study period will last 15 months of enrolment plus max.16 months of observation and Safety Follow-up.

9.2.1 Study Period

Study period will be divided to 3 observation phases:

- Retrospective data collection from the period of 1 to a maximum of 12 months prior to enrolment
- II. Prospective Observation Period, lasting a max. of 15 months
- III. Safety Follow-up, lasting 30 days after the end of the Observational Period

9.2.2 Selection and Number of Sites

In the participating countries, approximately 70 in-patient and out-patient investigative centers that routinely treat subjects with mCRC will have designated involvement in the study. Centers will include academic, public and private settings and will be distributed in diverse geographical regions within each country. Subject enrolment will last from the day of site opening until end of the study, with a total of 15 months for all participating countries. Sites will be eligible to participate in the study if they are listed among the sites to receive and administer panitumumab according to the formulary and will receive a target to recruit into the study based on the country level. Country Level enrolment will allow sufficient numbers to facilitate the representativeness of each country and to ensure appropriate level of data collection to support any applicable regulatory submissions. Each site will provide account of the number of patients receiving panitumumab in combination with chemotherapy as 1st line treatment during the last 12 months prior to site initiation.

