9.2.3 Subject/Healthcare Professional Eligibility

9.2.3.1 Inclusion Criteria

- I. Subject who received first infusion of panitumumab in combination with chemotherapy as 1st line treatment between 1 and 12 months before enrolment and who is continuing on treatment with panitumumab in combination with chemotherapy at the time of enrolment
- II. Subject with a record of WT RAS CRC diagnosis as per standard clinical practice
- III. Subject with metastatic carcinoma of the colon or rectum with at least one metastatic site recorded

Date: 29 April 2019 Page 26 of 64

IV. Subject with initially non resectable mCRC at the start of panitumumab plus chemotherapy treatment

- V. Subject who was diagnosed with a tumour, assessed by CT/MRI etc. prior to panitumumab plus chemotherapy initiation
- VI. Histologically or cytologically confirmed carcinoma of the colon or rectum as the primary site
- VII. Subject ≥ 18 years of age on the date of enrolment/ICF signature
- VIII. Subjects whose care will be managed primarily by the enrolling physician and/ or all records will be available from initiation of 1st line panitumumab plus chemotherapy treatment
- IX. Subject or subject's legally acceptable representative has provided informed consent

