9.7.2.3 Descriptive Analysis

9.7.2.3.1 Description of Study Enrolment

All eligible subjects' enrolled into the study will be included in the full analysis set and will be included in all summaries and analyses. To assess whether sites are representative cross country, summary statistics of site characteristics and the number of subjects enrolled in the study by site will be provided.

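### Sites recruit to a target with no rule on whom to invite, and the only patient count stops at site initiation, so the report cannot estimate what fraction of eligible patients was captured

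*Protocol*

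**What the plan says.** Protocol section 9.2.2 sets out how patients reach the study. Sites "will receive a target to recruit into the study based on the country level", and the section states that "Country Level enrolment will allow sufficient numbers to facilitate the representativeness of each country". It asks for a single patient number: "Each site will provide account of the number of patients receiving panitumumab in combination with chemotherapy as 1st line treatment during the last 12 months". The window closes at initiation: "1st line treatment during the last 12 months prior to site initiation". On timing it says: "Subject enrolment will last from the day of site opening until end of the study, with a total of 15 months for all participating countries".

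Inclusion criterion I (9.2.3.1) takes a "Subject who received first infusion of panitumumab in combination with chemotherapy as 1st line treatment between 1 and 12 months before enrolment" who is still on the combination at enrolment.

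The planned check on representativeness (9.7.2.3.1) is at site level: "summary statistics of site characteristics and the number of subjects enrolled in the study by site will be provided". Sections 9.2.2 and 9.9.2 add a mix of hospital types and a geographic spread. Section 9.9.1.1 discusses early cessation and survival, missing data, and reimbursement as sources of selection bias. It does not mention the investigator's choice among eligible patients.

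**The concern.** The primary objective is to describe patients and treatment patterns, with country as a reporting stratum. Section 7.2 says the data may indirectly support health technology assessments. In such a study the value of a proportion depends on who entered the sample.

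Two things are missing that only the sites can supply, so an analysis plan cannot add them later:

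- The protocol contains no instruction to invite eligible patients consecutively, or to invite all of them.
- It asks for no number of eligible, invited or declining patients that matches the enrolment period.

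The safeguards in 9.2.2, 9.7.2.3.1 and 9.9.2 bear on which centres take part. They do not bear on which patients within a centre are enrolled. If investigators tended to invite patients with a particular course, the description would shift, and the report would have no figure from which to judge by how much.

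**Working it through.** **Inputs from the protocol.** The count covers 12 months before initiation (9.2.2). Enrolment lasts 15 months in total (9.2.2). First infusion is 1 to 12 months before enrolment, with treatment ongoing (9.2.3.1). About 600 subjects are planned, with a 95% CI half-width of at most 4 percentage points overall (Abstract, Study Sample Size).

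**The plan's own figure.** The half-width at a proportion of 0.5 is 1.96 × √(0.25/600) = 4.0 percentage points. Solving for exactly 4 points gives n = 0.25 × (1.96/0.04)² ≈ 600. The stated precision reproduces, and this point does not affect it.

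**Period covered by the count.** Treat site opening and initiation as the same day (assumption). A patient enrolled t months after opening, with t from 0 to T, must have started between t − 12 and t − 1. Across the enrolment period, eligible start dates run from −12 to T − 1, a span of 12 + (T − 1) months. The count covers the first 12.

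- T = 15 (full period): 12/26 = 46%, leaving 14 months uncounted
- T = 12 (assumed): 12/23 = 52%
- T = 9 (assumed): 12/20 = 60%
- T = 6 (assumed): 12/17 = 71%

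These are shares of calendar start dates, not of patients.

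**Content of the count.** It takes in everyone receiving the combination during that year. That includes patients who had already stopped and patients who started too early to fall within 12 months of any possible enrolment date. Criterion I excludes both groups. The number enrolled divided by this count is therefore not a capture fraction, because the two numbers describe different sets of people.

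**What an unknown capture fraction could mean (illustration).** Let f be the fraction of eligible patients enrolled and d the difference in some characteristic between enrolled and non-enrolled eligible patients. The bias is (1 − f) × d. With d assumed at 10 percentage points:

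- f = 50%: 0.5 × 10 = 5 points
- f = 70%: 0.3 × 10 = 3 points
- f = 90%: 0.1 × 10 = 1 point

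The first two are of the same order as the 4-point overall precision. For one country, assuming an equal split over nine (600/9 ≈ 67), the half-width is 1.96 × √(0.25/67) ≈ 12 points, so sampling error would exceed a bias of this size there. The documents give neither f nor d.

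**The case against.** **The count may not be meant as a denominator.** It sits beside site eligibility and recruitment targets and reads naturally as a measure of site volume. This stands: the protocol never ties it to measuring capture, so it is not a denominator taken from the wrong period. What remains is that it is the only patient count in the plan and cannot serve that purpose.

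**Free choice is inferred from silence.** Nothing says that investigators may pick among eligible patients. Section 9.9 worries instead about finding enough of them, and if they are scarce, sites may enrol nearly all. Working instructions could also sit in the stand-alone documents that Appendix A lists, or in the interactive enrolment system of 9.1. This stands as a limit on the claim. A reader might infer that sites will hand-pick patients who are doing well, but the documents do not show that.

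**Part of the selection is built in and disclosed.** Requiring ongoing treatment already favours patients who tolerate it, and 9.9.1.1 admits a survival bias. That is selection by the criteria. It does not cover selection among patients who meet them.

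**The size is easily overstated.** A reader might take 46% as the coverage everywhere, but it holds only for a site open the full 15 months. A reader might also argue that, with 600/70 ≈ 9 subjects per site, a few selected patients distort a site's profile. No patient profile by site is planned; summaries are for the total and per country.

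**Charts of non-enrolled patients raise consent.** Section 10.1 requires written consent before a chart is used, where applicable. This stands against any split of non-enrolled patients by reason taken from their records, and the fix avoids one.

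**Conclusion.** The point holds as a gap in the design that is cheap to close, not as a demonstrated bias. Section 9.2.2 leaves the order of invitation open. Its only count omits every patient who starts after initiation, and it includes some who could never be eligible.

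At a site open for the full 15 months, 14 of 26 months of eligible start dates are uncounted. The gap is smaller at sites that open later. This rests on initiation and opening coinciding.

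The consequence is that the report can describe participating centres but cannot estimate the fraction of eligible patients captured within them. Whether that matters numerically is unknown. Under the assumed 10-point difference it ranges from 1 to 5 points as capture falls from 90% to 50%. The sample size and the stated precision are unaffected.

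**What to change.** 1. In 9.2.2, require sites to invite eligible patients consecutively, in order of clinic visit, until the target is met or enrolment ends. For sites already open, apply this going forward. If a stand-alone document already sets such a rule, cite it.
2. In 9.2.2, extend the existing count to all patients with a first infusion of first-line panitumumab plus chemotherapy from 12 months before initiation to 1 month before the site's last enrolment. Add aggregate numbers invited, declined and enrolled, where local rules allow.
3. In 9.7.2.3.1, report these numbers by site and by country.
4. In 9.9.1.1, name investigator selection among eligible patients as a possible bias.

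The cost is protocol wording, a small extra workload at sites that already owe a count, and less freedom in whom to invite. No visit or procedure is added. Aggregate counts bound the selection but do not show its direction, and the bounds can be wide: with fraction f captured, the range for a proportion among all eligible patients has width 1 − f, for example 30 points at 70% capture. The extended count still includes some patients who fail other criteria or had stopped before they could be invited, so the fraction derived from it should be described as approximate.

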9.2.3 Subject/Healthcare Professional Eligibility

9.2.3.1 Inclusion Criteria

- I. Subject who received first infusion of panitumumab in combination with chemotherapy as 1st line treatment between 1 and 12 months before enrolment and who is continuing on treatment with panitumumab in combination with chemotherapy at the time of enrolment
- II. Subject with a record of WT RAS CRC diagnosis as per standard clinical practice
- III. Subject with metastatic carcinoma of the colon or rectum with at least one metastatic site recorded

Date: 29 April 2019 Page 26 of 64

IV. Subject with initially non resectable mCRC at the start of panitumumab plus chemotherapy treatment

- V. Subject who was diagnosed with a tumour, assessed by CT/MRI etc. prior to panitumumab plus chemotherapy initiation
- VI. Histologically or cytologically confirmed carcinoma of the colon or rectum as the primary site
- VII. Subject ≥ 18 years of age on the date of enrolment/ICF signature
- VIII. Subjects whose care will be managed primarily by the enrolling physician and/ or all records will be available from initiation of 1st line panitumumab plus chemotherapy treatment
- IX. Subject or subject's legally acceptable representative has provided informed consent

9.2.3.2 Exclusion Criteria

- I. Subject with proven brain metastasis
- II. Subject with mCRC as a secondary malignancy
- III. Ongoing or planned concurrent participation in any interventional clinical trial

9.2.4 Matching

Not applicable

9.2.5 Baseline, Retrospective Data Collection and Enrolment Visit

The detailed schedule of procedures to be performed during the study is provided in Appendix E.

Baseline is defined as the date of the start of panitumumab in combination with chemotherapy. The decision on treatment with panitumumab should have been taken independently from the decision to study enrolment and prior to it.

The data will be abstracted from subject's medical records and entered into the electronic case report form (eCRF) by the Investigator or designee during the enrolment Visit (after the subject signed informed consent).

The required data should be collected where available and recorded as standard clinical practice, including but not limited to the following information:

- Demographics: age, sex
- Targeted medical history / comorbidities: chronic obstructive pulmonary disease (COPD), diabetes, other neoplasia, anaemia, hypertension, coronary disease/incident, obesity
- Physical measurement, including height and body weight

Date: 29 April 2019 Page 27 of 64

- Vital signs
- 1st line treatment data:
 - 1st line treatment choice and treatment goal
 - chemotherapy: selection of chemotherapeutic agents, dosage and interval
 - start date of therapy and total number of cycles
 - changes in dosing and reasons for changing (for example AEs) (dose changes related to the changes of body weight are not considered dose changes)
 - treatment interruption if longer than 30 days in one single interval and reasons for interruption
 - changes in biologic treatment (both chemotherapy and targeted therapy) for any reason
- Panitumumab administration:
 - dose and schedule
- Substance use
- Laboratory tests: haematology and chemistry prior to or at Baseline
- Reproductive status
- Eastern Cooperative Oncology Group (ECOG) performance status
- Disease history:
 - type of primary tumour diagnosed using all or any of the following methods: computer tomography (CT), magnetic resonance imaging (MRI), positron emission tomography (PET) and the date of diagnosis
 - site of primary tumour: rectum vs colon, right vs left colon
 - surgical procedures
 - lymph nodes: number and involvement
 - tumour node metastasis (TNM) stage
 - adjuvant chemotherapy, including regimen if applicable
 - sites of metastatic disease: liver, lung, other diagnosed by chest X rays, bone X rays, ultrasound assessments (any performed) or radio nuclear examinations
- Tumour evaluations:
 - evaluation and re evaluation / assessment (methods, criteria, timing Q2M), RECIST criteria (if available)
 - ETS at week 8 (if available, as per clinical practice) measured using all or any of the following methods: CT, MRI, PET
- Site characteristics.

Safety data will not be collected retrospectively, however side effects related to panitumumab treatment, and details of skin toxicity management will be collected as part of medical history.

Date: 29 April 2019 Page 28 of 64

The following key data will also be collected at Baseline where available. These data must originate from the time prior to the subjects' first dose of panitumumab in combination with chemotherapy:

 Method (incl. Brand name, if available) and date of RAS testing (test requested and result available), if available. Data on other biomarkers, if conducted, will also be collected.

9.2.6 Prospective Observation Period

The Prospective Observation Period will start at the enrolment Visit and subject visits should be registered on a monthly basis. Data will be collected on a monthly basis for 15 months during 1st line treatment administration. In case of earlier discontinuation of 1st line treatment, the data from maintenance treatment (other than 2nd line treatment) will be collected for the Observation Period of 15 months.

Data obtained during the 15-month Observation Period will be reported into the eCRF.

The following data will be collected on a monthly basis:

- Physical measurement
- Vital signs
- ADR events: type and duration of ADR incident; prophylaxis for skin toxicity, occurrence of skin toxicity and details of skin toxicity management using FACT EGFRI-18 QoL questionnaire (See Appendix F) if permitted in a country per local regulations.
- Concomitant medications
- 1st line treatment pattern including:
 - chemotherapy: drug, dosage and interval
 - changes in dosing and reasons for the change
 - treatment interruption if it is longer than 30 days in one single interval and reason of interruption
 - changes in biologic treatment (both chemotherapy and targeted therapy) for any reason
 - stop date and reason for treatment discontinuation.
- 2nd line treatment pattern including:
 - biological agents: drug name/s, dose and schedule
 - chemotherapy: drug name/s, dosage and interval
- Panitumumab administration:
 - dose and schedule
- Laboratory values: haematology and chemistry

Date: 29 April 2019 Page 29 of 64

- ECOG performance status
- Tumour evaluations:
 - evaluation and re evaluation / assessment (methods, criteria, timing Q2M), RECIST criteria (if available)
 - ETS at week 8 (if available, as per clinical practice) measured using all or any of the following methods: CT, MRI, PET
 - disease evaluation as routinely monitored (if different than RECIST criteria), including chest X rays, bone X rays, ultrasound assessments (any performed) or radio nuclear examinations
 - information about biomarker status (if available).

